5.4 Administration of Study Interventions

5.4.1 Randomization

To ensure that participants are balanced with respect to key variables, participants will be assigned to BSFT or TAU using an urn randomization procedure. Urn randomization procedures employ an algorithm that uses information about the composition of treatment groups to maximize the similarity of groups on specific variables (Stout et al., 1994). This procedure maintains random assignment but ensures comparability between the two conditions on key variables. The key variables that will be balanced in this study include:

- Ethnicity/race (African American, Hispanic, or other)
- Level of drug use at baseline (any drug diagnosis other than alcohol or tobacco, no drug diagnosis)

Randomization will be conducted using a standard telephone call-in system created by the Veteran's Affairs.

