10.2.6 Planned Post Hoc Analysis

In most hypotheses, HLM has been used to minimize the number of statistical tests per hypothesis. In the case of a significant effect of BSFT in any of these hypotheses, planned post-hoc tests will look at the time path of this difference and document when the simple differences are statistically significant.

An additional sequence of analyses will be done to address variability in the effect of BSFT. This will be accomplished by adding explanatory variables associated with the sites in the equations at Level 3 for the intercept and slope. For example, because TAU services are not standardized, additional planned analyses will be conducted to examine the effectiveness of BSFT compared to various types of TAU services (e.g., individual therapy, group therapy, day treatment, recreational treatment). These analyses will include full exploration of the planned characterization of TAU services at each CTP. These analyses will also examine if there are differential attrition rates in different types of TAU services, and if BSFT is more effective than TAU when controlling for different engagement and retention rates across TAU services. As such, these analyses will help to address the possibility that TAU is just as effective as BSFT for those cases that remain in treatment. In all of these analyses, referral from an institution for the treatment of drug use will be entered as a covariate.

Companion analyses will examine whether patient characteristics, after controlling for TAU differences, are related to effectiveness of the BSFT intervention. These will be accomplished by adding explanatory variables in the equations for Level 2 for the intercept and slope. Variables to be considered include: age, gender, ethnicity/race, level of drug use, primary drug of abuse, family type, and baseline levels of internalizing/externalizing problems, family and peer functioning. This will answer the question of for whom the intervention worked.

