Analysis. The analyses for Hypothesis 2b is identical to the hierarchical linear models (HLM) (Bryk & Raudenbush, 1992) used to test Hypothesis 1. It is anticipated that no link function will be necessary.

Hypothesis 2c: BSFT will be significantly more effective than TAU in decreasing sexually risky behaviors

Outcome variable. For Hypothesis 2c, the total score of the ‘HIV/Sex Risk Behaviors’ measure will be used as the outcome.

Analysis. The analyses for Hypothesis 2c is identical to the hierarchical linear models (HLM) (Bryk & Raudenbush, 1992) used to test Hypothesis 1. It is anticipated that no link function will be necessary. The composite measure will be constructed using the methodology described in hypothesis 2b applied to the items of the Risk Behavior Survey from the Common Assessments Battery.

Hypothesis 2d. BSFT will be significantly more effective than TAU in increasing prosocial activities.

Outcome Variable. A composite measure will be verified using confirmatory factor analysis. Scales to be included in the composite and confirmatory analysis are the ‘Conventional Activities of Friends’ scale of the Pittsburgh Youth Survey, and the (negatively weighted) ‘Peer Delinquency’ scale from the Pittsburgh Youth Survey.

Analysis. Hypothesis 2d will be analyzed as in Primary Hypothesis 1 using hierarchical linear models (HLM) (Bryk & Raudenbush, 1992). Again, the composite measure will be constructed using the methodology described in 2b.

Planned Post-hoc Analyses. Planned post-hoc analyses for the secondary hypotheses are identical to those explained above under the primary hypotheses. These analyses will attempt to explain the variability in the treatment effect.

Hypothesis 2e. BSFT will be significantly more effective than TAU in improving family functioning.

Outcome Variable. The four components of the ‘Parenting Practices Inventory’ will be used to create a composite for use in this analysis. The four component scales from the Parenting Practices Inventory are ‘Positive Parenting’, ‘Discipline Effectiveness,’ ‘Avoidance of Discipline’ and ‘Monitoring’ scales from the Pittsburgh Youth Survey (see Gorman-Smith et al., 1996).

Analysis. Hypothesis 4 will be analyzed as in Hypothesis 1 using hierarchical linear models (HLM) (Bryk & Raudenbush, 1992). Again, the composite measure will be constructed using the methods described in 2b, above.

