For these eight reasons, and, in accordance with the Data Safety Monitoring Board's SOP, presentation of primary and secondary effectiveness outcome data and other data not intended to evaluate safety will be presented for all treatment groups combined, further broken down by study node and by CTP (when more than one CTP per node). No statistical penalty will be taken for these blinded interim analyses of efficacy data that will be conducted for the sole purpose of assessing the acceptability of safety results.

Adverse event data and other data intended for the monitoring of safety will be presented to the DSMB in an unblinded fashion. Because the trial is not powered to demonstrate statistically significant differences in adverse events or other safety outcomes, p-values will not be calculated for any differences observed unless specifically requested by members of the Board to assist in the evaluation of a potential safety concern. No adjustments will be made to the efficacy analyses for the number of interim safety analyses in the final report.

Although an interim analysis of effectiveness data is not planned, the DSMB may feel that such analysis is necessary to permit proper evaluation of safety data. Should an unscheduled interim analysis of efficacy be necessary, the Board will specify the question, the analysis required, the critical

[name]

values for a decision and the statistical procedures necessary to control the overall type 1 error at $p < 0.05$. A protocol amendment will be included in the DSMB report of the analysis describing necessary changes in the statistical plan that result from the analysis.

Should the DSMB desire that an interim analysis plan be established prior to implementation of the trial, we would recommend a single interim analysis to take place after both 1) $\frac{1}{2}$ of the subjects have completed the 8 month follow-up and 2) at least 5 sites from have enrolled some number of subjects (to ensure stability in the estimates of treatment effect variability). The trial will enroll sites “waves.”

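### Section 10.2.6 promises that the patient-moderator analysis will settle who benefits from BSFT, which a look at about ten characteristics in 480 youths cannot do

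*Protocol*

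**What the plan says.** Protocol Section 10.2.6 describes companion analyses of whether patient characteristics are related to the effectiveness of BSFT. The method is "adding explanatory variables in the equations for Level 2 for the intercept and slope". Six candidate characteristics are named first: "age, gender, ethnicity/race, level of drug use, primary drug of abuse, family type". The list then adds four scores taken at baseline, two for internalizing and externalizing problems and two for how the family and the peer group function. The paragraph closes with "This will answer the question of for whom the intervention worked".

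Section 10.3 extends this: "Planned post-hoc analyses for the secondary hypotheses are identical to those explained above under the primary hypotheses".

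The same section treats its other analyses more cautiously. The time-path tests are run only after a significant BSFT effect. The therapist effect and the alternative drug-use outcomes are described as things to be explored. The patient-moderator paragraph carries no such condition or caveat.

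**The concern.** The problem is the affirmative closing sentence. It commits the trial to reading the moderator results as an answer, although the analysis looks at many characteristics and the sample was sized for an average effect. A chance finding on one characteristic could be reported as the group in which BSFT works. An absence of findings could be reported as evidence that BSFT works equally for everyone. At stake is what the trial may conclude about effect modification, not its primary conclusion.

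**Working it through.** **The plan's own power figures.** The protocol states no error rate or power for the moderator analysis. The nearest stated figures are in Section 10.4.1: 87%, 75% and 64% for small, moderate and large site variability, with J = 8, effective n = 57 and δ = .45. For a multisite random-effects test, F(1, J − 1) with noncentrality λ = Jδ²/(σ² + 4/n), at two-sided .05:

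- Jδ² = 8 × .45² = 1.62 and 4/57 = .0702.
- σ² = .05 (assumed; the value for small variability is not legible in the text): λ = 1.62/.1202 = 13.48, power 88.1%.
- σ² = .10: λ = 1.62/.1702 = 9.52, power 75.4%.
- σ² = .15: λ = 1.62/.2202 = 7.36, power 64.5%.

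These agree with the stated figures. They concern the average treatment effect only. Sections 10.4.2 and 10.4.3 give power within a CTP, and none is given for effect modification.

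**Number of moderator terms.** Section 10.2.6 names six variables (age, gender, ethnicity/race, level of drug use, primary drug, family type) and four baseline scores (internalizing, externalizing, family functioning, peer functioning), ten in all. Sections 10.1.1 and 10.2.1 already place most of these in the primary model as covariates. The new terms must therefore be products with BSFT, one in the intercept and one in the slope equation: 10 × 2 = 20. The list is open-ended. Ethnicity/race has three levels in Section 5.4.1, "Ethnicity/race (African American, Hispanic, or other", so 20 is a low count if categories are dummy-coded.

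**Chance of at least one false moderator, primary outcome.** Assume no true moderation and a two-sided .05 per test. For k independent tests the chance is 1 − .95^k.

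| Test format (assumed) | k | Chance of at least one |
|---|---|---|
| One joint 2-df test per characteristic, ten characteristics | 10 | 40.1% |
| The same, with internalizing/externalizing as one and family/peer as one | 8 | 33.7% |
| Separate terms, eight characteristics | 16 | 56.0% |
| Separate terms, ten characteristics | 20 | 64.2% |
| Separate terms, ethnicity as two dummies | 22 | 67.7% |
| Separate terms, several factors dummy-coded (levels assumed) | 26 to 28 | 74% to 76% |

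The expected number of false positives is 10 × .05 = 0.5 in the first row and 20 × .05 = 1.0 in the fourth.

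Tests on the same youths are correlated. Simulating 20 correlated z-tests, with assumed correlations of 0 to .3 between characteristics and 0 to .7 between intercept and slope terms, gives 52% to 64%.

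For comparison, a single joint test of all the terms has a 5% error rate by construction. A threshold of .05/20 = .0025 per term gives 4.9% for independent tests.

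**Power for a moderator.** Section 4.1 aims for approximately 100 females (Section 7.3 makes this a minimum) of 480. With equal arms, unit SD, no site variance and complete data, the interaction SE is √(4/n₁ + 4/n₂).

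- Gender, 100 and 380: SE = √(4/100 + 4/380) = .225. For an interaction of .45, .45/.225 = 2.00 and power is about 52%. For .25 it is about 20%. The interaction detectable with 80% power is .63.
- An evenly split characteristic, 240 and 240: SE = √(8/240) = .183. Power is about 69% for .45 and 28% for .25. The interaction detectable with 80% power is .51.

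An interaction of .45 is as large as the whole design effect. Site variability and attrition would lower these figures.

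**The case against.** Several arguments count against pressing this point hard, and most of them stand in part.

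- **The SAP may handle multiplicity.** A protocol commonly leaves the significance level, adjustment and test order for post hoc analyses to the SAP, which is not shown. The missing adjustment is therefore not itself a finding. But an adjustment made elsewhere would leave the definite sentence standing in the protocol.
- **A reader might infer that the trial would name a false subgroup more often than not.** The documents do not support this. The protocol states no rule that any significant term identifies a responder group, and it sets no alpha. Each characteristic enters both equations, so one joint test per characteristic is a natural reading, and that gives about 40%. For a continuous characteristic, a false positive would name an effect modifier, not strictly a subgroup.
- **A reader might infer that the analysis should be conditional on a significant Hypothesis 1.** This is a preference. Opposite effects can cancel in the average, and Section 10.2.6 itself allows for effects in opposite directions across sites.
- **A reader might infer that the results will steer which youths clinics offer BSFT.** No passage ties treatment allocation to the moderator results. Section 10.2 gives the aim as general applicability across community providers.
- **The context is already cautious.** The heading calls these analyses post hoc. Section 10.3 says of the secondary outcomes only that the analyses will try to explain variability in the treatment effect. Hypothesis 2a has no trajectory, so the count of 20 does not carry over to it. These points reduce the weight of the concern, but they do not change what the closing sentence claims.

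**Conclusion.** The point holds as one of interpretation. As written, Section 10.2.6 promises an answer that the design cannot give. With ten characteristics and an assumed .05 level, the chance of at least one false moderator on the primary outcome runs from about 40% (ten joint 2-df tests) to 64% (20 separate independent terms). It is somewhat lower if the terms are correlated or the characteristics are grouped, and higher with multi-category coding. Repeating the analyses for the secondary outcomes adds further opportunities for chance findings. In the other direction, a gender interaction of .45 SD has about 52% power under favourable assumptions, so a null result does not answer the question either.

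These figures rest on an alpha and a test format that the protocol does not state, so they show scale and are not operating characteristics of a stated rule. The conclusion does not depend on which format is chosen. The primary test and the sample size are untouched.

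**What to change.** In Section 10.2.6, replace the closing sentence with wording that the patient-moderator analyses are exploratory, may suggest for whom BSFT works and need confirmation in other data. For each outcome, report one joint test of all treatment-by-characteristic terms (intercept and slope together where there is a trajectory) as context for the individual moderators. State how many characteristics were examined. Apply the same wording in Section 10.3.

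Holm adjustment of individual moderators, or making them conditional on Hypothesis 1, is optional. Either would lower power that is already limited.

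The cost is a change of wording and one extra model comparison per outcome. No new data are needed. A joint test over about 20 terms may itself have little power against a single moderator, which is why it is proposed as context and not as a gate.

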10.3 Secondary Outcomes and Hypothesis

There are five categories of secondary outcomes: a) engaging adolescents and family members in treatment, b) decreasing externalizing problem behaviors, c) decreasing adolescent sexually risky behaviors, d) increasing adolescent prosocial activities (e.g., school, employment), and e) improving family functioning (e.g., parenting, parent-adolescent relations). Please note that these secondary outcomes are only measured at B1, T4, T8 and T12.

Hypothesis 2a: BSFT will be significantly more effective in engaging participants in treatment than will TAU.

Outcome Variable. Engagement is defined as attendance by adolescent and/or family members at a minimum of two therapy (treatment) sessions. For BSFT, these will be BSFT sessions, for TAU, these will be defined in a manner that is consistent with the services provided (e.g., individual, group or non-manualized family therapy, day treatment).

Analysis. Hypothesis 2 will be analyzed as in Hypothesis 1 using hierarchical linear models (HLM) (Bryk & Raudenbush, 1992). However, in this analysis a logistic link function will be used due to the 0-1 nature of the outcome. Note that because this outcome is not a time-related value, that trajectories are not involved, however all other levels of nesting described in the primary analysis are still in effect and therefore HLM is still the method of analysis. In planned post-hoc analysis

[name]

engagement of adolescents and family members (i.e., attendance in therapy sessions), specifically will be examined.

Hypothesis 2b. BSFT will be significantly more effective than TAU in decreasing externalizing problem behaviors.

Outcome Variable. For Hypothesis 2b, a composite of the following scales will be used: ‘Total Delinquency’ from the National Youth Survey; ‘Oppositional Defiant Disorder’ and ‘Conduct Problems’ from the Diagnostic Interview Schedule for Children-Predictive Scales, and the ‘Externalizing Scale’ from the Youth Self-Report. A confirmatory factor analysis will be conducted to determine that these scales measure a single construct. Reliability of this construct when loadings are constrained to be 1 will be calculated and if sufficient, equally weighted composite scores will be constructed. Otherwise, factor scores will be created using the estimated loadings and the resulting composite will be used to examine hypothesis 2b.

Analysis. The analyses for Hypothesis 2b is identical to the hierarchical linear models (HLM) (Bryk & Raudenbush, 1992) used to test Hypothesis 1. It is anticipated that no link function will be necessary.

Hypothesis 2c: BSFT will be significantly more effective than TAU in decreasing sexually risky behaviors

Outcome variable. For Hypothesis 2c, the total score of the ‘HIV/Sex Risk Behaviors’ measure will be used as the outcome.

Analysis. The analyses for Hypothesis 2c is identical to the hierarchical linear models (HLM) (Bryk & Raudenbush, 1992) used to test Hypothesis 1. It is anticipated that no link function will be necessary. The composite measure will be constructed using the methodology described in hypothesis 2b applied to the items of the Risk Behavior Survey from the Common Assessments Battery.

Hypothesis 2d. BSFT will be significantly more effective than TAU in increasing prosocial activities.

Outcome Variable. A composite measure will be verified using confirmatory factor analysis. Scales to be included in the composite and confirmatory analysis are the ‘Conventional Activities of Friends’ scale of the Pittsburgh Youth Survey, and the (negatively weighted) ‘Peer Delinquency’ scale from the Pittsburgh Youth Survey.

Analysis. Hypothesis 2d will be analyzed as in Primary Hypothesis 1 using hierarchical linear models (HLM) (Bryk & Raudenbush, 1992). Again, the composite measure will be constructed using the methodology described in 2b.

Planned Post-hoc Analyses. Planned post-hoc analyses for the secondary hypotheses are identical to those explained above under the primary hypotheses. These analyses will attempt to explain the variability in the treatment effect.

Hypothesis 2e. BSFT will be significantly more effective than TAU in improving family functioning.

Outcome Variable. The four components of the ‘Parenting Practices Inventory’ will be used to create a composite for use in this analysis. The four component scales from the Parenting Practices Inventory are ‘Positive Parenting’, ‘Discipline Effectiveness,’ ‘Avoidance of Discipline’ and ‘Monitoring’ scales from the Pittsburgh Youth Survey (see Gorman-Smith et al., 1996).

Analysis. Hypothesis 4 will be analyzed as in Hypothesis 1 using hierarchical linear models (HLM) (Bryk & Raudenbush, 1992). Again, the composite measure will be constructed using the methods described in 2b, above.

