Adolescent and family member reports on assessments will be kept strictly confidential, including confidential from each other. The only exceptions are in cases of imminent danger, including suicidality, homicidality, abuse or neglect. Similarly, self-reports, interviews, and biological data collected from an adolescent as part of the research protocol will not be shared with parents or any outside agency, unless in instances of suicidality, homicidality, abuse or neglect. This requirement applies in particular to protecting the release of research data to outside agencies (such as the juvenile justice system), which is of great importance when working with a “prison” population. The research assistant will remind participants about the confidentiality of reports as well as their limitations. Parent

[name]

guardians will be informed that information conveyed by adolescents during the assessments is strictly confidential, and that they will NOT have access to this information (except in the instances of imminent danger mentioned above). Adolescents will also receive the same assurances of confidentiality. Emphasizing confidentiality is particularly important for ensuring accurate reports of adolescent drug use and other problem behaviors. At each assessment time point (B1-T12), once the administration of the measures is finalized, Research Assistants will present the following statement to the adolescent: “I have faith that the information I have provided will be kept confidential”. Adolescents will rate this statement using a five-point Likert scale as follows: strongly agree, agree, neutral, disagree, and strongly disagree. This will allow proper monitoring for faith in confidentiality. Sometimes, as treatment progresses, faith in confidentiality of information increases, and adolescents report more drug use.

Baseline Assessments

Baseline assessments will be completed to assess functioning and behaviors prior to entering treatment. Table 1 shows the measures that are administered at baseline. Measures are briefly described below.

Post-randomization Assessments

Primary outcome assessments are conducted monthly and at 4-, 8-, and 12-months following randomization. Secondary outcome measures used in the baseline assessment are also administered at 4-, 8-, and 12-months following randomization as indicated in Table 1.

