7.7.1 Demographics

The CAB Demographic measure is used to characterize the participants. In addition, a family demographic form was added to provide information about aspects of the family that is not contained in the CAB and that may be useful in interpreting the results.

- CTN Demographics Form. The CTN Demographics Form (Common Assessment Battery).
- Parent Demographic Form. This 20-item questionnaire identifies who lives in the adolescent’s home, serve in important familial roles as well as identifies family composition/type and family household income.
- Family Demographic Form. This measure is an interview for parents/guardians at B1, T4, T8 and T12. The purpose of this measure is to identify who resides in the home with the adolescent as well as family members or other individuals that have regular contact with the adolescent. This form also tracks changes in family constitution along the study.

TABLE 1. MEASURES

INSTRUMENT	ADMIN MODE	PARENT TIME (MIN)	ADOL. TIME (MIN)		TIMEPOINT	DEMO-GRAPHICS	PSYCH FUNC.	DRUG USE	EXTERNALIZING BEHAVIOR	INTERNALIZING BEHAVIOR	FAMILY	PEER
CTN COMMON ASSESSMENT BATTERY												
CTN Baseline Demographics Form	Interview	--	10'		B1	X						
Urine drug screen	Assay	--	5'		Monthly, B1 - T12,			X				
Risk Behavior Survey	Interview	--	10'		B1, T4, T8 & T12				X			
Addiction Severity Index-Lite- Drug Abuse module only	Interview	10'	--		B1 & T12			X				

TABLE 1. (CONTINUED) MEASURES

INSTRUMENT	ADMIN MODE	PARENT TIME (MIN)	ADOL. TIME (MIN)		TIMEPOINT	DEMO-GRAPHICS	PSYCH FUNC.	DRUG USE	EXTERNALIZING BEHAVIOR	INTERNALIZING BEHAVIOR	FAMILY	PEER
PROTOCOL SPECIFIC ASSESSMENTS												
Parent Demographic Form	Interview	10'	--		B1, T4, T8, T12	X						
Family Demographic Form	Interview	5''			B1, T4, T8, T12	X						
DISC Predictive Scales	Interview	15'	15'		B1 & T12		X		X	X		
DISC SA	Interview	--	30'		B1 & T12							
Timeline Follow Back	Interview	--	30'		Monthly, B1 - T12,			X				
National Youth Survey	Interview	--	10'		B1, T4, T8 & T12				X			
Parenting Practices (Chicago Survey)	Self-report	20'	20'		B1, T4, T8 & T12						X	X
Family Environmental Scale	Self-report	5'	5'		B1, T4, T8 & T12						X	
Conventional Activities of friends (Pittsburgh survey)	Self-report	5'	5'		B1, T4, T8 & T12							X
Peer delinquency Scale	Self-report		5'		B1, T4, T8 & T12							X
Youth Self Report	Self-report	--	20'		B1, T4, T8 & T12				X	X		
Adverse Events+	Interview	5'	5'		B1, T4, T8 & T12							

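### The Hypothesis 2b composite includes DISC Predictive Scales that Table 1 schedules only at B1 and T12, so the planned growth model centred on T4 cannot be fitted to it as written

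*Protocol*

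**What the plan says.** **Outcome.** Section 10.3 states: "For Hypothesis 2b, a composite of the following scales will be used". The list is NYS Total Delinquency, Oppositional Defiant Disorder and Conduct Problems "from the Diagnostic Interview Schedule for Children-Predictive Scales, and the" Externalizing scale of the YSR. Section 7.7.4 also names the two DISC disorders, by parent and adolescent report, as indicators for Hypothesis 2b.

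**Timing in the analysis section.** Section 10.3 says of the secondary outcomes: "Please note that these secondary outcomes are only measured at B1, T4, T8 and T12".

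**Timing in the schedule.** In Table 1 (printed under section 7.7.1) the row "DISC Predictive Scales" carries the timepoints B1 and T12. The other two instruments in the composite read "National Youth Survey Interview -- 10' B1, T4, T8 & T12" and "Youth Self Report Self-report -- 20' B1, T4, T8 & T12". Section 7.6 says that secondary measures used at baseline "are also administered at 4-, 8-, and 12-months following randomization as indicated in Table 1", so follow-up administration is referred back to that table.

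**Model.** Section 10.3 continues: "The analyses for Hypothesis 2b is identical to the hierarchical linear models (HLM", pointing to the model for Hypothesis 1. Sections 10.2 and 10.2.1 fix that model: time is zero at T4, only times after baseline are outcomes, and the baseline value is a covariate. Section 10.2.4 bases the test on the BSFT coefficient at T4 and on the BSFT-by-time coefficient.

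**Missing data.** Section 10.1.1 uses the EM algorithm for items missing within a multi-item scale, does not impute missing outcome measures, and relies on maximum likelihood under missing at random.

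**The concern.** The composite, the schedule and the model are each stated, and they do not fit together. The model needs the outcome at several post-baseline visits. The schedule supplies all of its components at only one.

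An analyst following the protocol would have to improvise. Averaging whichever scales are present would give a score without DISC at T4 and T8 and with DISC at T12. A change in that score between T8 and T12 would mix change in behaviour with change in what is measured, and the slope would carry both. Dropping DISC, or using a factor model that tolerates absent indicators, would be a different outcome or an unstated method. If chosen after data are seen, it would be open to selection.

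If instead Table 1 is the mistaken entry, DISC data not collected at T4 and T8 cannot be recovered later.

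**Working it through.** The protocol gives no sample size, power or alpha for Hypothesis 2b, so there is no figure to reproduce. The check sets the schedule against the model.

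**Step 1: where the composite exists.**

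| Component | B1 | T4 | T8 | T12 |
|---|---|---|---|---|
| NYS Total Delinquency | yes | yes | yes | yes |
| YSR Externalizing | yes | yes | yes | yes |
| DISC Oppositional Defiant Disorder | yes | no | no | yes |
| DISC Conduct Problems | yes | no | no | yes |
| Full composite | yes | **no** | **no** | yes |

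B1 enters only as a covariate, so one outcome time remains: T12.

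**Step 2: fixed effects.** With a = months since T4, the fixed part of the model in section 10.2.3 is γ000 + γ100·BSFT + γ001·a + γ101·BSFT·a. (Section 10.2.4 prints other subscripts, but its wording describes the BSFT and BSFT-by-time terms, γ100 and γ101.) The design row is [1, BSFT, a, BSFT·a].

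- As planned, T4, T8 and T12 give a = 0, 4 and 8. The rank is 4 of 4.
- Under Table 1, T12 alone gives a = 8. The two distinct rows are [1, 0, 8, 0] for TAU and [1, 1, 8, 8] for BSFT. The rank is 2 of 4. The one estimable treatment contrast is γ100 + 8·γ101, the difference at T12.

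**Step 3: person-level variances.** A random intercept, a random slope, their covariance and a residual make 4 parameters. With m outcome times there are m(m + 1)/2 variance and covariance elements.

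| Outcome times | m | Elements | Parameters | Fixed-effect rank |
|---|---|---|---|---|
| T4, T8, T12 (planned) | 3 | 6 | 4 | 4 of 4 |
| T12 only (Table 1) | 1 | 1 | 4 | 2 of 4 |
| B1 and T12 (B1 used as an outcome, against section 10.2.1) | 2 | 3 | 4 | 4 of 4 |

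In the last row the T4 difference would only be a straight-line interpolation. T4 lies 4/12 = 1/3 of the way from B1 to T12, so it equals 2/3 of the B1 difference plus 1/3 of the T12 difference. No T4 data inform it.

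**Step 4: actual visit dates.** Section 10.2.5 allows time to vary between people. Scatter of visit dates around T12 would raise the rank formally. The slope would then rest on who came early or late to the 12-month visit, and the T4 effect on extrapolating back 8 months. That is not the planned estimate.

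**Step 5: the measurement check.** Section 10.3 wants a confirmatory factor analysis to show a single construct, and section 10.1.1 plans similar checks at each follow-up. At T4 and T8 there are two indicators, hence 2·3/2 = 3 variances and covariances. A one-factor model with free loadings has 4 parameters (two loadings and two residual variances, with the factor variance fixed), so it is under-identified. With loadings fixed at 1 it has 3 parameters and 0 degrees of freedom, so its fit cannot be tested.

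**The case against.** **Table 1 may be the error.** Sections 3.0, 7.6 and 10.3 all give secondary outcomes four assessment times. This stands: the documents do not show which entry is wrong. Section 7.6 does defer to Table 1, so as written the table governs. The point is the contradiction, not a ruling for one side.

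**A growth analysis of externalizing behaviour remains possible.** This also stands. The NYS and YSR scales are scheduled at every secondary visit. A reader might infer that Hypothesis 2b cannot be tested longitudinally at all; that goes too far. What cannot be done is to fit the stated model to the stated composite.

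**The missing-data rules might cover it.** They do not. Maximum likelihood handles a missed assessment; it does not define a composite whose parts were never scheduled. A reader might infer that EM would fill in the DISC part for everyone at T4 and T8. Section 10.1.1 limits EM to items missing within scales and says that missing outcome measures are not imputed, so the protocol does not call for this.

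**How much of the composite is missing.** Two of the four named scales invite the reading that half the outcome is absent. The text does not fix that share. Section 7.7.4 draws on parent and adolescent report, which could enter separately, and section 10.3 allows estimated loadings instead of equal weights. What can be said is that every DISC component is unscheduled at T4 and T8.

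**Section 7.7.8.** Its mention of baseline use might be read as showing that DISC is a baseline-only measure. It concerns psychiatric functioning and possible covariates, and Table 1 itself lists T12, so it does not settle the schedule.

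**Conclusion.** The contradiction is real. Under Table 1 the full Hypothesis 2b composite exists at 1 of 3 post-baseline secondary visits, and the design has rank 2 of 4. Of the two treatment coefficients to be tested, neither can be estimated separately; only γ100 + 8·γ101 can.

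This assumes that Table 1 describes what is collected, that all listed scales are needed to form the composite, and that the Hypothesis 1 model applies unchanged. If the first assumption fails, the planned model is estimable and the error lies in Table 1.

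The defect is confined to one of five secondary hypotheses. The primary outcome, its model and its sample size are untouched.

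**What to change.** Reconcile Table 1 with sections 7.7.4 and 10.3, by one of two routes.

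1. **If Table 1 is right.** Define the repeated 2b outcome from NYS Total Delinquency and YSR Externalizing only. Put each on a common scale fixed at baseline (for example, the pooled B1 mean and SD, used at all visits) and weight them equally. The planned model then has outcomes at T4, T8 and T12, with rank 4 of 4 and 6 covariance elements for 4 parameters. Report DISC Oppositional Defiant Disorder and Conduct Problems at T12, adjusted for B1, as supportive outcomes outside the main 2b test, so that one hypothesis does not become three tests. Correct the timing sentence in section 10.3 accordingly.
2. **If DISC is in fact collected at T4 and T8.** Correct the Table 1 row and keep the composite.

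**Cost.** The first route changes wording and needs no new data. DISC leaves the repeated composite. With two indicators the single-construct factor model can no longer be tested for fit, and loadings cannot be estimated at a single visit, so equal weights replace the protocol's factor-score fallback. The second route costs only the table correction if the data are already being collected. The choice should be fixed before any comparison by treatment arm.
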